2.7.3 Statistical hypothesis, model, and method of analysis

There are few secondary endpoints for which we are measuring the effect at EOT as mentioned in [Section 2.7.2](#).

Here, EOT is defined as last assessment of a discontinued or completed patient irrespective of time point; EOT is defined as the last assessment during the follow-up for patients who started the follow-up but didn't complete the study; EOT is the last assessment before discontinuation for the patients who discontinued the trial before 12 months; EOT is the last assessment for patients that discontinued from study at month 12 but not enter in the follow-up period. The change from baseline to EOT is defined as the difference between the EOT and baseline values i.e. Change from baseline = EOT – baseline.

2.7.4 Handling of missing values/censoring/discontinuations

2.7.4.1 FACIT-Fatigue

There are 13 items. Negatively worded items are reverse scored prior to summing. Add the scores together, multiply by 13 and then divide by the number of items answered. A total score of <30 indicates severe fatigue. The higher the total score the better the quality of life. Total score can vary from 0 to 52.

In cases some answers are missing, a total score is prorated from the score of the answered items, so long as more than 50% of the items (i.e., at least 7 of 13) were answered.

FAT_N = N(OF HI7 HI12 AN1-AN5 AN7 AN8 AN12 AN14-AN16);

IF (FAT_N/13 >0.50) THEN Fatigue = SUM(OF HI7 HI12 AN1-AN5 AN7 AN8 AN12 AN14-AN16)*13/(FAT_N);

Further details on the FACIT-Fatigue scoring is provided at:

<http://www.facit.org/FACITOrg/Questionnaires>

http://www.physio-pedia.com/Functional_Assessment_of_Chronic_Illness_Therapy

2.7.4.2 FACT-Th6

There are 6 questions in FACT-Th6 questionnaires. The calculation of total score is done by multiplying the sum of the item scores by the number of items in the subscale, then divide by the number of items answered. This produces the subscale score. FACT-Th6 score will only be computed if we have no more than 2 missing responses.

2.7.4.3 SF-36v2

The details for calculation of the score and handling of missing responses in SF-36 v2 is provided in Appendix 2.

2.7.4.4 TSQM-9

The details of scoring and handling of missing values is provided in the appendix. In the three domains, each require at least 2 non-missing responses for calculating the score. Otherwise the overall response will be considered as missing.

2.7.4.5 GP5

Missing responses for GP5 will not be imputed.

2.8 Safety analyses

Safety summary tables include all data (from the on-treatment period) with the exception of baseline data which will also be summarized where appropriate.

The on-treatment period lasts from the date of first dose of eltrombopag to 30 days after the date of the last dose of eltrombopag for patients who discontinued the study. For ongoing patients (not applicable for final CSR analysis), the on-treatment period lasts from first dose of eltrombopag to 30 days after the cut-off date. For all safety analyses the safety set will be used.

2.8.1 Adverse events (AEs)

Coding of AEs

Adverse events will be coded using the latest version of MedDRA at the time of the analysis.

Grading of AEs

AEs will be assessed according to the Common Terminology Criteria for Adverse Events (CTCAE) version 4.03.

The CTCAE represents a comprehensive grading system for reporting the acute and late effects of cancer treatments. CTCAE grading is by definition a 5-point scale generally corresponding to mild (as reported in AE CRF in severity grade variable), moderate (as reported in AE CRF

in severity grade variable), severe (as reported in AE CRF in severity grade variable or “Hospitalization (initial or prolonged)” or “Disability or permanent damage” or “Congenital Anomaly or birth defect” or “Other serious (important medical events)”), life threatening, and death. This grading system inherently places a value on the importance of an event, although there is not necessarily proportionality among grades (a grade 2 is not necessarily twice as bad as a grade 1).

AE summaries

AE summaries will include all AEs occurring during on-treatment period. All AEs collected in the AE (e)CRF page will be listed along with the information collected on those AEs, e.g. AE relationship to study drug, AE outcome etc. AEs starting during the post-treatment period will be flagged in the listings. All information obtained on adverse events will be displayed by patient. Summary tables for adverse events (AEs) will include only AEs that started or worsened during the on-treatment period, the **treatment-emergent** AEs (TEAEs).

TEAEs will be summarized by number and percentage of patients having at least one AE, having at least one AE in each primary system organ class (SOC) and for each preferred term (PT) using MedDRA coding. A patient with multiple occurrences of an AE will be counted only once in the respective AE category. A patient with multiple CTCAE grades for the same preferred term will be summarized under the maximum CTCAE grade recorded for the event. AE with missing CTCAE grade will be included in the ‘All grades’ column of the summary tables.

The incidence of TEAEs will be summarized by system organ class (SOC) and or preferred term, severity based on the CTCAE grades, type of adverse event and relation to eltrombopag.

In AE summaries the primary system organ class will be presented alphabetically and the preferred terms will be sorted within primary SOC in descending frequency. The sort order for the preferred term will be based on their frequency.

The following adverse event summaries will be produced; overview of adverse events and deaths, AEs by SOC and PT, summarized by relationship, seriousness (SAEs and non-SAEs), leading to treatment discontinuation, leading to dose interruption/adjustment, requiring additional therapy and leading to fatal outcome. In addition, a summary of serious and non-serious adverse events with number of occurrences will be produced (an occurrence is defined as >1 day between start and prior end date of record of same preferred term) as per EudraCT requirements.

All AEs and SAEs will be listed and those collected during the pre-treatment (from day of patient’s informed consent to the day before first dose of eltrombopag) and post-treatment period will be flagged.

A patient with multiple AEs within a primary SOC is only counted once towards the total of the primary SOC.

Summaries of AEs, SAEs, SAEs with fatal outcome, AEs leading to discontinuation and overview of AEs will be provided for the month 12 on-treatment period.

The overview of AE will be provided by SRoT_M12 status.

2.8.1.1 Adverse events of special interest / grouping of AEs

Serious adverse events, AEs leading to discontinuation, AEs leading to dose adjustment and adverse events of special interest (AESI) which includes bleeding events during the on-treatment period will be tabulated.

Specific groupings of AESI will be considered and the number of patients with at least one event in each grouping will be reported. Such groups consists of AEs for which there is a specific clinical interest in connection with eltrombopag treatment or AEs which are similar in nature (although not identical). Note that certain AEs may be reported within multiple groupings/AESIs.

AESIs are defined by MedDRA terms. Definition for retrieval and maintenance is done in the electronic case retrieval sheet (eCRS).

The incidence of AESIs will be summarized by SOC and Preferred Term (PT).

The AESIs as specified in the latest version of the case retrieval sheet (CRS) at the time of analysis will be used.

Summaries of AESIs will be provided for the month 12 on-treatment period.

2.8.2 Deaths

Separate summaries for on-treatment and all deaths (on-treatment and post-treatment [starting at day 30+1 after last dose of eltrombopag]) will be produced by system organ class and preferred term.

All deaths will be listed and those collected during the pre-treatment (from day of patient's informed consent to the day before first dose of eltrombopag) and post-treatment period will be flagged.

2.8.3 Laboratory data

Grading of laboratory values will be assigned programmatically as per the CTCAE version 4.03. The calculation of CTCAE grades will be based on the observed laboratory values only, clinical assessments will not be taken into account.

CTCAE Grade 0 will be assigned for all non-missing values not graded as 1 or higher. Grade 5 will not be used. For laboratory tests where grades are not defined by CTCAE version 4.03, results will be categorized as low/normal/high based on laboratory normal ranges.

The following summaries will be generated separately for key hematology and biochemistry tests laboratory tests:

- Shift tables comparing baseline to the worst on-treatment value. Each patient will be counted only once for the worst grade observed post-baseline.
- For laboratory tests where grades are not defined, shift tables using the low/normal/high/ (low and high) classification to compare baseline to the worst on-treatment value will be used.

Imputation rules

CTC grading for blood differentials is based on absolute values. However, this data may not be reported as absolute counts but rather as percentage of WBC.

If laboratory values are provided as ‘<X’ (i.e. below limit of detection) or ‘>X’, prior to conversion of laboratory values to SI unit, these numeric values are set to X.

The following rules will be applied to derive the WBC differential counts when only percentages are available for a xxx differential

$$\text{xxx count} = (\text{WBC count}) * (\text{xxx \%value} / 100)$$

Further derivation of laboratory parameters might be required for CTCAE grading. For instance, corrected calcium can be derived using the reported total calcium value and albumin at the same assessment using the following formula:

$$\text{Corrected Calcium (mg/dL)} = \text{Calcium (mg/dL)} - 0.8 [\text{Albumin (g/dL)} - 4]$$

In order to apply the above formula, albumin values in g/L will be converted to g/dL by multiplying by 0.1, calcium values in mmol/L will be converted to mg/dL by dividing by 0.2495. For calculation of laboratory CTC grades 0 and 1, the normal range for derived corrected calcium is set to the same limits (in mg/dL) as for calcium.

CTC grades for the derived absolute WBC differential counts (neutrophils, lymphocytes, etc.) and corrected calcium will be assigned.

Data analysis

On analyzing laboratory results, data from all sources (central and local laboratories) will be combined. The summaries will include all assessments available for the lab parameter collected no later than 30 days after the last study treatment administration date.

The following summaries will be produced for hematology and biochemistry laboratory data (by laboratory parameter and treatment):

- Worst post-baseline CTC grade (regardless of the baseline status). Each patient will be counted only for the worst grade observed post-baseline.
- Shift tables using CTC grades to compare baseline to the worst on-treatment value
- For laboratory tests where CTC grades are not defined, shift tables using the low/normal/high (low and high) classification to compare baseline to the worst on-treatment value.
- Trends of lab parameter values over time (baseline and selected on-treatment timepoints) should be displayed via boxplots based on time windows and corresponding tables displaying the statistics used for the box plots by the selected time points.
- The following listings will be produced for the laboratory data:
Listings of all laboratory data, with CTC grades and classification relative to the laboratory normal range. Lab data collected during the post-treatment period will be flagged.

Listing of all CTC grade 3 or 4 laboratory toxicities

Liver function parameters

Liver function parameters of interest are total bilirubin (TBIL), ALT, AST and alkaline phosphatase (ALP).

The number (%) of patients with worst post-baseline values will be summarized:

- ALT or AST >3xULN

- ALT or AST >5xULN
- ALT or AST >8xULN
- ALT or AST >10xULN
- ALT or AST >20xULN
- TBL >2xULN
- TBL >3xULN
- ALT or AST >3xULN & TBL >2xULN
- ALT or AST >3xULN & TBL >2xULN & ALP <2xULN

Potential Hy's Law events are defined as those patients with concurrent occurrence of AST or ALT >3xULN and TBL >2xULN and ALP <2xULN in the same assessment sample during the on-treatment period. Further medical review must be conducted to assess potential confounding factor such as liver metastasis, liver function at baseline etc.

2.8.4 Other safety data

Data on ECG, vital sign, weight, ocular findings and bleeding events will be summarized descriptively, listed and flagged as appropriate. Any significant findings will be documented as AEs and reported as such.

2.8.4.1 ECG

12-lead ECGs, including QTcF (Fridericia's correction), mean heart rate (HR), PR-, QT- and QRS-durations will be presented by number and percentages of patients.

Where ECG replicates are provided for an assessment, the average of the ECG parameters at that assessment will be used in the analyses.

The number (%) of patients with notable values will be presented.

Table 2-1 Notable criteria for ECG parameters

Parameter	Notable low value	Notable high value
QTcF		New value of >450 and \leq 480 ms
		New value of >480 and \leq 500 ms
		New value of >500 ms
		Increase from baseline of >30 ms to \leq 60 ms
		Increase from baseline of >60 ms
Heart rate	Heart rate Decrease >25% from baseline and to a value <50 bpm	Increase >25% from baseline and to a value >100 bpm

Parameter	Notable low value	Notable high value
PR		Increase >25% from baseline and to a value >200 ms New value of >200 ms
QRS		Increase >25% from baseline and to a value >120 ms New value of >120 ms

A listing of all ECG assessments will be produced. Notable values as well as values measured outside of on-treatment period will be flagged in the listings.

2.8.4.2 Vital signs

Vital sign assessments are performed in order to characterize basic body function. The following parameters will be collected: height (cm, inch), weight (kg, pound), body temperature (°C, Fahrenheit), position, pulse (beats/minute), systolic and diastolic blood pressure (mmHg). The number (%) of patients with notable values will be presented.

[figure not shown]
Table 2-2 Notable criteria for vital signs

Vital sign (unit)	Notable low value	Notable high value
Weight (kg)	decrease ≥10% from baseline	increase ≥10% from baseline
Body temperature (°C)	--	≥39.1
Pulse rate (bpm)	≤50 and decrease from baseline of >25%	≥100 and increase from baseline of >25%
Systolic blood pressure (mmHg)	≤90 and decrease from baseline of ≥20	≥180 and increase from baseline of ≥20
Diastolic blood pressure (mmHg)	≤50 and decrease from baseline of ≥15	≥105 and increase from baseline of ≥15

A listing of all vital sign assessments will be produced and notable values will be flagged. Assessments collected outside of on-treatment period will be flagged.

2.8.4.3 Bleeding scales

Safety analysis set will be used reporting WHO and ITP bleeding events.

WHO Bleeding Scale

The WHO bleeding scale is a measure of bleeding severity with the following grades: Grade 0: no bleeding, Grade 1: mild bleeding, Grade 2: moderate bleeding, Grade 3 gross bleeding and

Grade 4: debilitating blood loss. The number and percent of subjects within each grade will be summarized at each time point, Grade 0 versus those with Grades 1-4 as well as Grade 0-1 versus those with Grades 2-4.

ITP Bleeding Score

The ITP Bleeding Score is an assessment of the bleeding severity in each of the following anatomical locations: Skin: petechiae, Skin: ecchymosis, Oral, Epistaxis, Ocular, Gastrointestinal, Genitourinary, Gynecological (Females only), Pulmonary and Intracerebral Hemorrhage. Severity is graded using scores 0, 1 and 2. The number and percentage of subjects in each grade at each time point will be presented by anatomical location for the ITP bleeding score assessments.

2.8.4.4 Bleeding adverse events used in efficacy analyses

All Adverse event (AEs) will be taken from the ae.sas dataset and exported as an Excel file. The clinical team will review the records captured in an Excel spreadsheet and mark with a 'Y' in new variable 'bleed_flag', those terms which are considered as bleeding AEs. Bleeding events on or before Day 7 are not considered in the efficacy derivations and will be programmatically excluded.

Once the database has locked the data will be rechecked again for any changes or new data that needs flagging.

The spreadsheet will contain three (3) tabs, the first tab is the final tab used in the analysis. The second and third tabs are used by the clinical team to flag the bleeding records and provide comments.

The first tab contains the following variables: reported term for the adverse event (AETERM), dictionary-derived term (AEDECOD), bleeding flag(Bleed_flag), the second tab contain the same variables with clinical team comments. Third tab contain additional variables to document decision making: unique subject identifier (USUBJID), reported term for the adverse event (AETERM), dictionary-derived term (AEDECOD, AEDECOD = 'Thrombocytopenia') and comments.

The spreadsheet will be imported into the programming environment (GPS) and merged with the patient data for the analysis where bleeding events will be filtered by the value 'Y' for the variable 'Bleed_flag' using the first tab. The EXCEL document will be stored in CREDI in the study folder ETB115J2411/Administrative Files (study level)/RAP or RAMP Meeting and in GPS in the study folder CETB115J\CETB115J2411\csr_1\util for primary CSR and folder CETB115J\CETB115J2411\csr_2\util for final CSR.

2.8.4.5 Ocular findings

Descriptors at Baseline, week 25 and EOT will be provided for body system examined and findings by eye. Frequencies and percentages will be provided for each time point. Listings will be provided.

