Eltrombopag administration can cause hepatobiliary laboratory abnormalities, severe hepatotoxicity and potentially fatal liver injury. In the controlled clinical studies in chronic ITP with eltrombopag, increases in serum alanine aminotransferase (ALT), aspartate aminotransferase (AST), and bilirubin were observed. Exercise caution when administering eltrombopag to patients with hepatic disease.

[figure not shown]
Hepatotoxicity will be monitored through serum alanine aminotransferase (ALT), aspartate aminotransferase (AST), and bilirubin levels as described in [Section 8.4.2](#) and additional investigations as clinically indicated. In case hepatobiliary abnormalities are observed, follow the guidelines in [Section 10.2.1](#).

Thrombotic / Thromboembolic complications

In eltrombopag clinical trials in ITP, thromboembolic events were observed at low and normal platelet counts. Caution must be used when administering eltrombopag to patients with known risk factors for thromboembolism including but not limited to inherited (e.g., Factor V Leiden) or acquired risk factors (e.g., ATIII deficiency, antiphospholipid syndrome), patients with prolonged periods of immobilization, malignancies, contraceptives and hormone replacement therapy, surgery/trauma, obesity and smoking. Platelet counts must be closely monitored and dose modifications must be made in accordance with parameters provided in the protocol. The risks of thromboembolism and any of the following complications versus the benefit of improved platelet counts must be evaluated by the Investigator for each patient with known risks of thromboembolic events.

Ophthalmic changes

Cataracts were observed in toxicology studies of eltrombopag in rodents. The data from the double-blind and open label ITP and HORT studies, as well as data from the LENS study and the Phase II HCV study did not suggest an increased risk of cataract development in patients treated with eltrombopag. This conclusion was supported by the blinded, independent ocular safety data review from the Clinical Events Committee (CEC). In the pooled data from the Phase III HCV studies (ENABLE studies), where patients received up to 57 weeks of eltrombopag at doses up to 100mg, there was a numerically higher incidence of cataracts in the eltrombopag treatment group compared with the placebo group.

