Ophthalmologic monitoring defined per protocol must be performed and investigational treatment (eltrombopag) discontinued in case of suspected cataract development or worsening or in case of retinal hemorrhages.

Benefits Associated with Eltrombopag Use

Eltrombopag is an oral TPO-RA indicated for the treatment of chronic ITP. It has a well-established efficacy and safety profile with evidence of improved QoL responses in addition to improvement in platelet counts.

Eltrombopag has been approved in over 100 countries for the treatment of chronic immune (idiopathic) thrombocytopenia in patients aged 1 year and above who are refractory to other treatments (e.g. corticosteroids, immunoglobulins).

Eltrombopag has been shown to be superior to placebo in raising and maintaining platelet count above $50 \times 10^9/L$ for 6 months with a significant reduction in bleeding symptoms in previously treated chronic ITP patients. Eltrombopag also enabled more patients to reduce/discontinue concomitant (corticosteroid) medication use (RAISE Study) ([Cheng 2011](#)).

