8.4.1 Ophthalmic examination

The ophthalmic exam should include the retina, blood vessels, optic disc/nerve. If the presence of a cataract(s) is suspected, a slit lamp examination is required. Ophthalmic exams will be performed at visits according to [Table 8-1](#).

Significant findings that were present prior to the signing of informed consent must be included in the Medical History page of the patient's eCRF. Significant new findings that begin or worsen after informed consent must be recorded on the AE page of the patient's eCRF.

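### The eye-exam table gives only per-eye frequencies at each time point, so it cannot separate new or worsened findings from pre-existing ones, and the adverse event tables close that gap only in part

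*SAP*

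**What the plan says.** SAP 2.8.4.5 has three sentences on the eye exams. The opening one reads "Descriptors at Baseline, week 25 and EOT will be provided for body system examined and findings by eye". The second asks for counts with percentages at every time point, and the third for listings. The section names no comparison with baseline, no count of patients with a new or worsened finding, and no denominator.

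Other sections bear on the same data:

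- **Protocol 4.6** gives the reason for the exams. In the pooled Phase III hepatitis C studies "there was a numerically higher incidence of cataracts in the eltrombopag treatment group compared with the placebo group", and study drug is to be "discontinued in case of suspected cataract development or worsening or in case of retinal hemorrhages".
- **Protocol 8.4.1** sets two recording routes. For old findings: "Significant findings that were present prior to the signing of informed consent must be included in the Medical History page". For later ones: "Significant new findings that begin or worsen after informed consent must be recorded on the AE page".
- **SAP 2.8.4**, which covers ocular findings among others, says "Any significant findings will be documented as AEs and reported as such".
- **SAP 2.8.1** tabulates, by patient, adverse events that began or got worse in the on-treatment period. **SAP 2.1.1** ends that period 30 days after the last non-zero dose for patients who have completed or left the study.

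**The concern.** The protocol's ocular concern is development or worsening of cataract, which is a change within a patient. A percentage per time point measures prevalence. A cataract present at entry is counted again at each later exam, and worsening shows only if the recorded descriptor changes category.

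Pre-existing findings are plausible here. Entry is open from 18 years with no upper limit (protocol 5.1), the highest age-specific incidence of ITP is above 60 years (protocol 1.1), and the SAP's age bands run to 85 and over (SAP 2.3.2). For laboratory tests the SAP already plans shift tables from baseline to worst on-treatment value (SAP 2.8.3).

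What is at stake is whether the scheduled exams, the systematic source of eye data, yield a tabulated count of patients with new or worsened findings.

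**Working it through.** The documents give no prevalence, incidence or denominator for eye findings, so there is no stated figure to reproduce. The check compares sections and then gives an illustration.

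**1. What each output can show**

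| Output | Separates new from pre-existing? | Limit |
|---|---|---|
| Eye table (SAP 2.8.4.5) | No | Per eye, per time point, no stated denominator |
| Listings (SAP 2.8.4.5) | Yes, by reading patient by patient | No count |
| Adverse event tables (SAP 2.8.1) | Yes | Site must consider the finding significant; on-treatment period only |

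**2. Who falls outside the adverse event tables**

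Week 53 Day 1 is study day 52 × 7 + 1 = 365. The on-treatment period runs to last dose + 30 days inclusive. A finding that starts on day 365 is therefore post-treatment if last dose + 30 < 365, that is, if the last dose fell before day 335. Patients who taper off and stay off are the group the trial aims to produce, so this is not a rare situation by design.

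One qualification applies. For patients still ongoing at the primary cut-off, SAP 2.1.1 extends the on-treatment period to the cut-off date, so such a finding could be tabulated in the primary CSR. In the final CSR no patient is ongoing, and it would be listed and flagged only.

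**3. Does that week 53 exam enter the eye table?**

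- SAP 2.1.1 (multiple assessments) admits an end-of-treatment assessment only within 30 days of last treatment.
- SAP 2.8 confines safety tables to the on-treatment period, apart from baseline.
- SAP 2.7.3, to which SAP 2.1.1 refers for the EOT derivation, takes the last assessment whenever it falls.

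Under the first two rules the exam is left out; under the third it is included. If it is left out, a finding first seen there enters neither summary table in the final CSR.

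**4. Illustration (all inputs assumed, none from the documents)**

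Let b = baseline prevalence, i = incidence among those free of the finding at baseline, and a0 and a1 = EOT exam attendance without and with the baseline finding. Then

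EOT percentage = [(1 − b)·a0·i + b·a1] / [(1 − b)·a0 + b·a1].

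With b = 10% and i = 3%:

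- a0 = a1: 0.9 × 0.03 + 0.1 = 12.7%, a change of +2.7 points.
- a0 = 85%, a1 = 60%: (0.02295 + 0.06)/(0.765 + 0.06) = 0.08295/0.825 = 10.1%, a change of about +0.1.
- a0 = 60%, a1 = 85%: (0.0162 + 0.085)/(0.54 + 0.085) = 0.1012/0.625 = 16.2%, a change of +6.2.

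For b from 5 to 20% and i from 3 to 5%, the extremes are:

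- b = 20%, i = 3%, attendance 85%/60%: 0.1404/0.80 = 17.55%, a change of about −2.5.
- b = 20%, i = 5%, attendance 60%/85%: 0.194/0.65 = 29.8%, a change of +9.8.

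With equal attendance the change is i(1 − b): 2.4 to 2.9 points for i = 3%, and 4.0 to 4.8 for i = 5%. A paired table would return i itself, provided attendance does not depend on the new finding. The sums are per patient, whereas the planned table is per eye.

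**The case against.** The strongest reply is that the plan as a whole already handles this. Significant pre-existing findings go to Medical History and significant new or worsened ones to the AE page, and the treatment-emergent tables then count patients. A suspected cataract requires a slit lamp exam (protocol 8.4.1) and triggers the discontinuation provision in protocol 4.6, so a site would hardly call it insignificant. This largely stands for cataract on treatment. A reader might infer that new cataract is confounded with pre-existing cataract throughout the safety reporting; the documents do not support that. What remains is lesser findings and findings after the 30-day limit.

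A reader might also infer that dropout will hide new cases. Nothing in the documents says that attendance depends on baseline eye status. With equal attendance the table shows most of the rise, and under SAP 2.7.3 EOT is not a fixed visit with a shrinking set. The eye-exam rows of protocol Table 8-1 are not visible in the text available, so attendance by visit cannot be inferred.

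Nor is the eye table the only safety display without a baseline comparison. Body temperature has a fixed threshold, the liver categories use worst post-baseline values, and the bleeding scales are frequencies by time point. Protocol 4.6 also says that the ITP and several other studies did not suggest a raised cataract risk. Table shells and special-interest groupings are in separate documents, so a shift table may exist there. Finally, with a single arm, even a paired table could not attribute a cataract to the drug rather than to age or prior steroids. All of this lowers the weight of the point without removing it.

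**Conclusion.** The point holds in limited form. The eye table in SAP 2.8.4.5 is cross-sectional and cannot by itself separate new or worsened findings from old ones. The adverse event tables fill much of the gap, but they depend on the site's view of significance. In the final CSR they also omit findings that start more than 30 days after the last dose. The SAP is unclear on whether a late EOT exam enters the eye table at all.

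Severity is minor: this is a descriptive safety display, with no effect on the primary endpoint or error rates. The attendance figures illustrate what the table cannot rule out. They do not estimate bias in this trial, and the bias is small if attendance does not depend on baseline status.

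**What to change.** In SAP 2.8.4.5:

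1. Add a patient-level shift table from baseline to worst post-baseline exam, using the worse eye.
2. Report the number (%) of patients with a new or worsened finding among those with a baseline and at least one later exam, and the number not examined.
3. Include exams more than 30 days after the last dose, flagged as off-treatment.
4. State which EOT rule (SAP 2.1.1 and 2.8, or SAP 2.7.3) governs eye exams.

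Keep the visit frequencies, listings and adverse event tables. The cost is one table from data already collected and one clarifying sentence. No procedure, visit or clinical rule changes.
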